- 4) All groups will be randomly assigned to receive the CHAMPION intervention or be an enhanced treatment as usual (ETAU) (control site). If they are assigned to CHAMPION, then they will agree to participate in a one-year biweekly (26 session) tele-mentoring program (approximately 1.25 hours each session). They will receive AMA Category 1 PRA CME credit hours (or corresponding CEU) for each session they attend and take the evaluation post-test for the session. CME participants will have to complete an evaluation to receive the credits. This process will be automated, and the University of Maryland Department of Faculty Affairs is partnering with us to provide the CME credits.

We will attempt to enroll OMHCs and clinics from all geographic regions and counties in the State of Maryland. Our goal is to enroll at least two OMHC clinics per county (one randomized to each condition). If we do not get OMHC representation from all counties, then we will open recruitment up to other clinics to apply for participation in the study. We will place an emphasis on underserved and rural areas of Maryland including those with a prominent African-American population; this is a cornerstone to our application. The State of Maryland is unique and well suited for studying and focusing on this minority population. We will have a formal application process, which will be used to select the clinics. Based on the high demand of getting the POC device, the demand for telemedicine for consultation and the demand to get clozapine training (based on our pilot data) we will recommend that the clinics and prescribers/clinical team meet the following criteria:

In our initial outreach/recruitment efforts, we will focus on recruiting clinics from rural counties in order to ensure that we have adequate OMHC representation from rural counties. We will complete this initial outreach effort in the first nine months. Once we enroll these clinics, then we will open recruitment to clinics in non-rural counties.

METHODS

Overview of the Study Design

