Sites included in the CHAMPION will receive the POC ANC device to use during the 12-month study (and for 12 months post intervention) as well as access to clozapine consultation as described in the ETAU condition for 12 months during the intervention and 12 months follow-up. In addition, approximately half of the CHAMPION sites/individuals will receive biweekly ECHO telementoring education sessions. These telementoring sessions will occur simultaneously for all intervention sites and may consist of one or two identical sessions during the week. Each session will consist of a 15-20-minute didactic period on specific topics which will be followed by approximately 1 hour of site supplied case and patient consultations. All the prescribers and the clinicians at the sites are welcome to attend the online session even if they enroll for study inclusion or not. Attendance will be tracked by the study team at the beginning of each session.

The session will conclude with a discussion and question and answer period. At the end of the session the team of clozapine experts will provide a written summary of treatment recommendations regarding the cases. Each CHAMPION session will have at least one clozapine expert delivering the didactic topic and at least 2 additional clozapine experts providing mentoring for the case-based consultation session. This will allow us to call upon the diverse group of experts in our proposed study personnel. We will complement the sessions with dissemination of any relevant publications, toolkits and tips.

Enhanced Treatment as Usual (ETAU) Condition and Justification

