Second, we will disseminate a centralized MPRC phone number and email contact to all 60 sites and individual prescribers for questions and consultative questions for clozapine starting at the CHAMPION randomization and continuing throughout the entire study period. At the conclusion of the entire grant funding we will post all ECHO sessions and make them available to the ETau sites.

Medicaid Data and Security

We will be getting Medicaid Data from the Hilltop Institute www.hilltopinstitute.org

The Hilltop Institute at the University of Maryland, Baltimore County (UMBC), is a non-partisan health research organization dedicated to advancing the health and wellbeing of people and communities. Hilltop conducts research, analysis, and evaluations on behalf of government agencies, foundations, and nonprofit organizations at the national, state, and local levels. Hilltop is committed to addressing complex issues through informed, objective, and innovative research and analysis.

Formed in 1994 as the Center for Health Program Development and Management in a unique collaboration with the Maryland Medicaid program, Hilltop was instrumental in the 1997 launch of HealthChoice, Maryland's Medicaid managed care program. Since its inception, Hilltop has maintained a nationally recognized partnership with the Maryland Department of Health to analyze state health policies and develop solutions for the Maryland Medicaid program.

Hilltop developed and manages a data warehouse containing Maryland's Medicaid claims and encounter data. Hilltop processes and warehouses data on service utilization by more than 1,200,000 Medicaid enrollees and Medicaid payments totaling over \$7 billion. Hilltop currently processes and archives more than 12 million records each month. These records are used to generate standardized and customized reviews of Maryland's Medicaid system. Among Maryland Medicaid enrollees are approximately 105,000 individuals who are also eligible for Medicare (Medicare-Medicaid enrollees). Since 2002, CMS has provided Hilltop with Medicare claims corresponding to those Medicare-Medicaid enrollees, which Hilltop refines and maintains. Hilltop is also expert in linking Medicare and Medicaid data to study issues that affect Medicare-Medicaid enrollees.

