b. Persistence to clozapine: Incident episodes of clozapine prescriptions will be identified by a 90 day look back period to identify a new episode of care. Persistence will be measured as the duration of the clozapine episode (in days) from the date of the first prescription record until the first gap of more than 45 days between prescriptions. Prescribing gaps will be calculated by first adding the days' supply to the dispensing date of each prescription to identify the date the prescription should be exhausted. Days that the patient is hospitalized will not be included in the calculation of episode duration. The first gap in prescribing of 46 days or more will be considered a discontinuation of the medication. An episode will only be right censored at the study endpoint, otherwise an episode can continue into the next time period. If a person has more than 1 episode of clozapine use during any time period, we will select the first episode.

Specific Aim 2: We will measure two educational outcomes: self-reported competence of prescribers/clinical team in using clozapine and knowledge associated with clozapine treatment. These will both be measured before and after the 12-month intervention period. These outcomes have been selected, because they are measurable and pilot data has already established that prescribers/clinical team will rate competence and answer questions on clozapine knowledge. In addition, we will pilot-test all questions and review the self-reported competence measure prior to the administration of the CHAMPION intervention.

a. Competence: Our measurement of competence will be based upon self-report assessment guided by Bandura's theory of self-efficacy (2, 3) and we are using a definition of competence as "the perceived self-efficacy rating of one's judgment to use clozapine"(2, 4). We will use a Visual Analog Scale (VAS) (0-100 mm) will serve as the primary outcome. Self-reported competence ratings will be evaluated for the overall use of clozapine and for each of the CHAMPION session topic areas. The VAS format has been found to be superior

CHAMPION PROTOCOL

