- 1) All participating sites will receive the POC ANC monitoring device. Athelas, the company will give each clinic at no charge and will help with sites for Medicaid billing so that sites can receive compensation for patients enrolled
- 2) All participating sites and individual prescribers will receive a centralized phone number and email for questions and consultation advice from the clozapine team
- 3) All participating sites will receive a laptop to ensure that, if randomized, they can participate in the telementoring CHAMPION sessions and if not randomized, has a means to complete the baseline and endpoint assessments and use for watching CHAMPION sessions when granted permission at the end of this study.

CHAMPION PROTOCOL

- 4) All prescriber participants that complete the baseline and 12-month competence and knowledge assessments will receive compensation for their time and effort to complete these assessments. For other team members participating (nonprescriber) knowledge and competence is optional. They will also receive compensation for time and effort.
- 5) All prescribers/clinical team randomized to CHAMPION can get 1.25 PRA Category 1 CME (or equivalent CEU credits) for participation. These will be available online through <https://cloud-cme.com>
- 6) All sites randomized to the CHAMPION will receive a stipend for snacks and drinks and organizing the CHAMPION sessions.
- 7) All sites will receive the Clozapine Handbook authored by Jonathan Meyer and Stephen Stahl.

Thus, we feel as if we have created an exciting opportunity for sites to participate and have several enhanced pieces included to maximize recruitment and eliminate the logistics of getting weekly ANC blood draws.

The prescribers/clinical team that are randomized to the CHAMPION have the benefit of improving knowledge and self-reported competence with clozapine through active discussion, interactions and cases. Others have reported the benefits of the social environment for the prescribers/clinical team. They are included together in one virtual room where everyone can interact. This social environment has benefits of camaraderie and satisfaction. Other benefits reported have been increased career satisfaction and improved staff interactions and communication. Lastly, the benefits include time savings on complex cases that would involve coordination for referral or phone calls under other circumstances.

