However, the indirect benefits to patients with serious mental illness and psychotic disorders in the State of Maryland are more considerable, as we believe that this study will increase prescriber self-reported competence and use of this superior antipsychotic medication. Patients may receive clozapine trials or be maintained more successfully than in the past. This could improve outcomes and may decrease hospitalizations and emergency room visits. It may lead to better job productivity and a host of other possible outcomes known to be associated with the path to remission and recovery. Also, unnecessary treatments with non-evidence-based treatments and long wait times for care could all be improved.

While financial compensation will be provided for the time and effort that participants provide and a stipend to the sites to organize snacks at the time of the CHAMPION, this is not considered a benefit of study participation.

Importance of the Knowledge to Be Gained

The risks that this study poses to participants are reasonable in relation to the anticipated benefits and potential heuristic value of the research. This study has the potential to improve clozapine prescribing, improve lives of many patients and decrease overall health system costs. We will learn if an ECHO intervention, CHAMPION, is effective for improving clozapine prescribing and we will understand if this effect can be mediated by prescriber self-reported competence scores. Given the importance of the information to be gained and the low risks, we feel this project has a high importance on knowledge to be gained.

We believe the risks of this study are far outweighed by the potential benefits to the participants and their patients with schizophrenia and that this will demonstrate an effective and sustainable way to improve the treatment of these patients

Data and Safety Monitoring Plan

CHAMPION PROTOCOL

This study puts forth a randomized double-blind trial where prescribers/clinical team of antipsychotic medications will be the enrolled population. The study is an educational intervention and no biophysiological intervention will be performed; being a minimal risk study. No Data Safety Monitoring Board (DSMB) is required but the PI and team will monitor this study as described below.

Roles and Responsibilities

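### The trial is labelled double-blind, but participants and session leaders cannot be blind; the measure exposed is the 12-month self-rated competence score (one H3 outcome and the H4 mediator).

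*Combined protocol and SAP*

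**What the plan says.** The only statement on blinding is in the Data and Safety Monitoring Plan, in the paragraph explaining why no monitoring board is needed: "This study puts forth a randomized double-blind trial where prescribers/clinical team of antipsychotic medications will be the enrolled population".

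Other sections describe the following.

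- **Recruitment steps, item 4:** "If they are assigned to CHAMPION, then they will agree to participate in a one-year biweekly (26 session) tele-mentoring program".
- **CHAMPION Intervention Condition:** the experts who teach and mentor come from the study team ("This will allow us to call upon the diverse group of experts in our proposed study personnel"), and "Attendance will be tracked by the study team at the beginning of each session".
- **Benefits to Maximize Enrollment, item 5:** "All prescribers/clinical team randomized to CHAMPION can get 1.25 PRA Category 1 CME".
- **ETAU section:** control sites get the device and access to consultation. On the sessions it says: "At the conclusion of the entire grant funding we will post all ECHO sessions and make them available to the ETau sites". Item 3 of the benefits list gives one purpose of the laptop at sites not assigned to CHAMPION as "use for watching CHAMPION sessions when granted permission at the end of this study".
- **Specific Aim 2, a. Competence:** "Our measurement of competence will be based upon self-report assessment", on a 0-100 mm visual analogue scale. The change in this score is one of two H3 outcomes, and its 12-month value is the H4 mediator.
- **Randomization Procedures:** assignment follows the baseline assessments.

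No section describes a sham or attention-control programme, or the masking of participants, staff, data programmers or analysts.

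**The concern.** Double-blind is a property that readers use to judge how far to trust a subjective outcome. Here one H3 outcome and the H4 mediator are participants' ratings of themselves, given after a year in which they knew whether they were in a programme meant to raise those ratings. If the label reaches a report, the competence effect, and the mediation result built on it, may be trusted more than the design allows. The label also leaves a practical question unanswered: whether anyone who derives or analyses the prescription outcomes is kept unaware of arm.

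**Working it through.** **1. Can each party be blind under the described procedures?**

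| Party | What the plan describes | Blind? |
|---|---|---|
| CHAMPION participants | Agree to the sessions once assigned; attendance taken; CME credit | No |
| ETAU participants | Device and consultation; recordings only after the grant ends | No |
| Session leaders | Study personnel deliver the live sessions | No |
| Data programmers, analysts | No statement | Not described |

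The label is therefore wrong for the first three rows. For the fourth, the documents are silent.

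**2. Does any calculation use the label?** Under Power, the stated N is 254, with h = 0.39, two-sided alpha 0.05, power 0.80, ICC 0.01 and clusters of 4 to 5. The usual formula for h = 0.39 gives 104 per arm, or 208. The design effect is 1 + (m - 1) × 0.01, that is 1.03 for m = 4 and 1.04 for m = 5. Dividing by the 85% data-availability assumption:

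- m = 4: 208 × 1.03 / 0.85 = 252.05, rounded up to 253
- m = 5: 208 × 1.04 / 0.85 = 254.49, rounded up to 255

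The stated 254 is reproduced, and blinding plays no part in it. The models for H1 to H4 do not mention it either.

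**3. Does baseline adjustment help?** Let t be the true effect on competence and s the shift in the 12-month rating that comes only from knowing one's arm. Baseline precedes assignment and so carries none of s. The adjusted difference between arms therefore estimates t + s, and s remains in full.

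**4. What follows for H4?** In a linear product-of-coefficients model, write the indirect effect as a × b. If s is the same for everyone in CHAMPION, path a becomes a + s and path b, estimated within arm, is unchanged. The indirect effect becomes (a + s) × b, so it is off by s × b, with the opposite change in the direct effect. If s differs between people, path b is distorted too, and neither the direction nor the size can be derived from the documents.

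**5. How large could the H3 effect be?** The documents give no value of s, so these values are assumptions. Take t = 0, m = 4.5 (design effect 1.035), no baseline adjustment, and a single two-sided test at 0.05 without the false-discovery-rate step. With n per arm, SE = sqrt(2 × 1.035 / n) in SD units, and the rejection probability is Φ(s/SE - 1.96) + Φ(-s/SE - 1.96). For N = 254, n = 127 and SE = 0.128. At s = 0.2, s/SE = 1.57 and the probability is 0.347.

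| Assumed s (SD) | N = 254 | N = 278 | N = 300 |
|---|---|---|---|
| 0 | 5% | 5% | 5% |
| 0.1 | 12% | 13% | 14% |
| 0.2 | 35% | 37% | 40% |
| 0.3 | 65% | 69% | 72% |

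Here 278 is the approximate number of prescribers that the HMIS section reports as included, and 300 is the target. The table shows sensitivity to s. It does not estimate s.

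**6. Are the outcome rules settled enough that masking would add nothing?** Primary Outcomes, item a, sets a pre-intervention period of 12 months. The HMIS section sets January 1, 2020 to July 31, 2021, which is 12 + 7 = 19 months. Item a links prescriptions to prescribers by NPI but does not say how to count a patient treated by several enrolled prescribers. At least two choices are therefore open.

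**The case against.** The case for leaving this alone has real strength.

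- The label occurs once, in a monitoring section. The design sections call the trial randomised and controlled, and nothing statistical depends on blinding. This stands, and it limits the point to a wrong description and an unacknowledged risk of bias.
- The plan calls competence self-reported throughout and defines it as perceived self-efficacy. A higher self-rating after training is thus partly the intended effect. This also stands. It means s cannot be cleanly separated from t, but it does not make the rating blinded.
- Live teaching cannot be masked from those taught. That is true, and it is a reason to describe the trial as open.
- Most claims rules are already written: denominator, look-back, gap length, censoring, first episode. This stands in part; the two open choices in step 6 remain.
- The intervention ended in August 2022, so new wording cannot change how the 12-month ratings were given. That is true. It can still change how they are reported.

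A reader might go further and infer that nobody in the trial is blind. The documents do not support that. Medicaid records come from an outside institute, HMIS staff code the hospital records, neither list of data elements includes an arm variable, and whether those staff or the analysts know the arms is not stated. A reader might also take the anticipated effect above 0.8 as a sign of inflated self-rating. Under Power, that figure covers the scored knowledge test as well as competence, so it shows no such thing.

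**Conclusion.** The point holds in limited form. The plan attributes to the trial a property that its design cannot have for participants and session leaders, and it describes no masking of outcome derivation or analysis. The exposed measure is the 12-month self-rated competence score, as one H3 outcome and as the H4 mediator; adjustment for baseline does not protect it. The knowledge half of H3 is a scored 52-item test and is much less exposed.

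It would be tempting to conclude that the primary result is compromised. The documents do not support that: H1 and H2 come from prescription records, so self-rating bias does not reach them directly.

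The size of any bias cannot be computed from the documents. The percentages in step 5 rest on assumed shifts and the plan's ICC of 0.01, and they do not raise the severity. Severity is low.

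**What to change.** 1. In the Data and Safety Monitoring Plan, replace double-blind with open-label, randomised by site or individual, and state who, if anyone, is masked.
2. For outcome-file work not yet done, build the Medicaid and HMIS files with arm codes withheld until three rules are locked: the pre-intervention period (reconciling 12 and 19 months), the episode definition, and the attribution of a patient shared by enrolled prescribers. Linkage by NPI can go ahead meanwhile.
3. Report H3 competence and the H4 mediation result as based on unblinded self-report, and place the knowledge score beside them.

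The cost is a few sentences, a coded arm variable for the programmer, and a less favourable description of the design. No further data or staff are needed.
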